5. PRELIMINARY TABULATIONS

All subjects who provide informed consent will be accounted for in this study. Regularly generated enrollment reports will describe:

- Number of subjects consented, eligible, and randomized by site
- Ongoing study status of all randomized subjects
- Reasons for ineligibility
- Protocol deviations
- Early study completers

Subject data will also be summarized by treatment group (combined 3K3A-APC vs. placebo & individual dose groups vs. placebo) with respect to important demographic characteristics. Distribution of categorical variables will be tabulated by treatment group. Continuous variables will be summarized as mean, standard deviation, minimum, and maximum by treatment group and overall. Variables to be collected will include:

- Demographic Characteristics and Baseline Measurements
 - Gender
 - Race
 - Ethnicity
 - Age
 - Years of Education
 - Hand Preference
 - Height (cm)
 - Platelet Count
 - History of Diabetes
 - History of Hypertension
- Baseline Stroke Characteristics & Timeline
 - NIHSS Prior to Recanalization Therapy
 - NIHSS Eligibility
 - Recanalization Therapy
 - mRS
 - Time from Stroke Onset to First Therapy
 - If tPA Only, Time from Stroke Onset to tPA Initiation
 - If IAT Only, Time from Stroke Onset to First Skin Puncture

- If IAT & tPA, Time from Stroke Onset to tPA Initiation or First Skin Puncture (Whichever Occurred First)

6. ANALYSIS POPULATIONS

Since the primary objective aims to estimate a maximum tolerated dose, no formal testing will be involved. All analyses to address the key secondary objectives will be conducted at the 0.05 significance level. The analysis population of interest will differ depending on the objectives of any particular analysis.

6.1. Primary Analysis

Any given subject who receives only one dose of study drug and does not experience a DLT will not be included in the CRM calculation. Thus, the primary analysis involving the CRM will utilize a modified intent-to-treat (mITT) approach, with subjects considered evaluable for the model if they are a confirmed randomization (receive at least one dose of study treatment) and either:

- Receive two or more doses of study medication
- Have a confirmed DLT

6.2. Secondary PK Analysis Population

The PK population includes all subjects who have sufficient data for PK analysis, and who have not been excluded from analysis for protocol deviations (or other study-related events) that could impact the calculation or interpretation of the pharmacokinetic parameters (such as getting too much heparin or receiving a blood transfusion).

6.3. Secondary Bleed Rate (Hemorrhage & Microbleeds) Analysis

The secondary bleeding analysis will be based on the results of the Day 30 MRI scans. Correspondingly, the analysis population for this secondary analysis will include all subjects who had a Day 30 scan collected.

6.4. Safety Analysis

All safety analyses will be implemented using an ITT approach, defined as all subjects who are randomized and receive at least one dose of study medication.

7. PRIMARY ANALYSIS

The primary objective of the RHAPSODY study is to evaluate the safety of multiple ascending intravenous (IV) doses of 3K3A-APC following tPA administration, mechanical thrombectomy, or both in subjects who have experienced moderate to severe acute hemispheric ischemic stroke. Safety will be assessed by defining dose limiting toxicities (DLTs), which will be graded using the National Cancer Institute (NCI) Common Terminology Criteria for Adverse Events (CTCAE), Version 4.03. DLTs will be modeled using the continual reassessment method (CRM) to make the determination on which, if any, dose to bring forward to future clinical studies. The primary endpoint analysis will make use of Bayesian methods for estimating the probability of a DLT at each of the doses under investigation.

When designing a CRM, O'Quigley et al (1990) recommend using a single-parameter dose-response model, $\psi(x_i^*, a)$, which is the probability of a toxicity at dose x_i^* for some unknown parameter, a , which defines the shape of the dose-toxicity function. Here, the probability of a DLT at dose x_i^* can be estimated using $\psi(x_i^*, \hat{a})$. For this study, a hyperbolic tangent dose-response model will be used, in which:

$$\psi(x_i^*, a) = \left\{ \frac{\tanh(x_i^*) + 1}{2} \right\}^a .$$

The CRM requires specification of the prior probabilities of a DLT at each of the investigational doses of 3K3A-APC under consideration. Based on a best estimate from the literature and previous studies (Wahlgreen et al, 2007; Hacke et al, 2008; Berkhemer et al, 2015; Campbell et al, 2015; Goyal et al, 2015; Saver et al, 2015), the four dose levels will be assigned prior probabilities of toxicity as indicated in Table 1 below.

Table 1. Assumed Prior Probabilities of Toxicity at Four Dose Levels Considered for the Study

Dose Level (µg/kg)	120	240	360	540
Prior Probability of a Toxicity	5%	7%	9%	11%

Each study participant will be assessed for DLT occurrence. A subject may either experience a DLT or reach the end of the DLT observation period without experiencing a DLT. For subjects that reach the end of the observation period without experiencing a DLT, the independent medical monitor (IMM) will perform a final review to either confirm no DLT has occurred or to identify potential DLTs for consideration. If either a site or the IMM report a potential DLT, the event will be adjudicated by the safety review committee (SRC).

After each evaluable subject in a cohort is adjudicated by the SRC as having or not having a DLT, the CRM will be updated by an unblinded study statistician and independently verified by a second unblinded study statistician. Specifically, the posterior mean of a will be re-estimated using the prior probabilities from Table 1 and all evaluable data for each cohort of subjects. Subsequently, the posterior probabilities of observing a DLT at each 3K3A-APC dose, $(x_{120}, x_{240}, x_{360}, x_{540})$, can be calculated by solving the above equation for:

$$\psi(x_i^*, \hat{a}), i = 120, 240, 360, 540.$$

Based upon that estimate, the largest dose with estimated toxicity probability, $\psi(x_i^*, \hat{a})$, less than or equal to 10% will be allocated to the next cohort of randomized participants. If this dose is more than one level higher than the previous dose allocated, the dose will only be increased one level. Dose de-escalation is not subject to any restrictions. There are 22 cohorts of four subjects each planned, but fewer may be enrolled should the study meet any of the stopping criteria.

In summary, the CRM model will proceed as follows:

- Enroll the first 4 subjects into cohort 1.
 - Treat one of the four subjects (chosen randomly) with placebo.
 - Treat the other three subjects with the lowest dose: 120 µg/kg.
 - Observe the number of subjects (out of the three treated subjects) that have a DLT per the study DLT definition.
 - Determine the number of evaluable subjects in the cohort. Any given subject who receives only one dose of study drug and does not experience a DLT will not be considered “evaluable”, and will not be included in the CRM calculation (i.e., for subjects with no DLT observed, two or more doses will need to be administered to be included).
 - Based upon the observed information from the evaluable subjects in the cohort, refit the assumed dose-response curve.
- Initially (through version 7.1 of the protocol), the re-estimated dose-response curve using all cohorts enrolled to date was then used to determine the highest dose level of the four under consideration that has an estimated probability of toxicity less than or equal to 10%.
 - The next cohort of subjects is treated at the dose level specified above – unless the chosen dose level is more than one level higher than the current level. If so, treat the next cohort of subjects at the next dose level above the current level.
- Based on a DSMB recommendation, this process was changed as of version 8.0 of the protocol. The basic process proceeds as described above, but once all subjects in a given cohort (n) have been enrolled, data from all prior cohorts (cohort 1, cohort 2, ..., cohort $n-1$) are used to determine the dose level of cohort $n+1$.
 - If enrollment is rapid such that both cohort ($n-1$) and cohort (n) are filled and awaiting DLT review, new subjects enrolled will be randomized to placebo until cohort ($n-1$) has been reviewed. (For example, if both cohort 13 and 14 are filled and awaiting review, subjects will be randomized to placebo until cohort 13 is closed and the model is rerun to determine the dose for cohort 15).
- Repeat the process.

At the conclusion of the study, the MTD will be selected using the rules specified above for the implementation of the CRM model. Specifically, the model will be run a final time using all observed data and the MTD will be defined as the highest dose with an estimated DLT rate of 10% or less based on that final model. The study will stop once the first of the following criteria have been met:

- The maximum number of cohorts (22) has been observed.

- If at any time after half of the cohorts (11) have been observed, two consecutive iterations suggest a 15% or higher toxicity rate at the lowest dose (stop for safety).
- If the study proceeds straight to the highest dose, and then observes 9 successive cohorts at the highest dose with no observed toxicity (stop and declare the highest dose the MTD).
 - Through simulation, it was determined that it would extremely unlikely to observe no DLTs after 9 successive cohorts if the true toxicity rate were 10%. Thus, after 9 cohorts we would have sufficiently determined that all doses under consideration are safe and early stopping would be justified.

Much of the process for implementing the selection of dose for each subsequent cohort of subjects has been automated. Once the DLT status for all evaluable subjects in a cohort is complete, the IWRS will notify both statisticians via email that a new cohort is available for analysis. At that point, the primary statisticians will independently complete the dose recommendation process. The statistician who submits the initial dose recommendation will be referred to as the initial statistician, while the statistician who submits the dose recommendation second will be referred to as the validation statistician. The initial statistician will enter the production database and save the table of DLTs for each cohort as a SAS table, to ensure that each dose recommendation can be reproduced at any time during or after the conduct of the study. In parallel fashion, both the initial and validation statisticians will run a SAS program that details the selection of the next dose and enter their selected dose for the next cohort of subjects into the study website. Once both statisticians enter the next dose recommendation and provided the two recommendations match, the randomization table will re-open and participants will be randomized to the newly recommended dose or placebo in a 3:1 ratio. If the two doses do not agree, the IWRS notifies the statisticians of a dose match error via email, and the process is repeated until a new dose recommendation is verified for the next cohort.

A list of backup statisticians will also be maintained. These individuals should be capable of serving in this capacity if either or both of the primary statisticians are unable to perform the tasks outlined below. It is the responsibility of the primary statisticians to place the backup statisticians 'on call' should the primary statisticians know of an upcoming period of unavailability.

Final CRM results will be displayed, by cohort, in the following format:

Table 2. CRM Cohort Toxicity Estimates

Cohort	Selected Dose (µg/kg)	# of Evaluable Subjects	# of DLTs	Toxicity Estimates			
				120 (µg/kg)	240 (µg/kg)	360 (µg/kg)	540 (µg/kg)
Priors							
1	120	X	X	XX.X%			
2	XXX	X	X	XX.X%			
...			
22	XXX	X	X	XX.X%			

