- Initially (through version 7.1. of the protocol), the re-estimated dose-response curve using all cohorts enrolled to date was then used to determine the highest dose level of the four under consideration that has an estimated probability of toxicity less than or equal to 10%
 - The next cohort of subjects is treated at the dose level specified above unless the chosen dose level is more than one level higher than the current level. If so, treat the next cohort of subjects at the next dose level above the current level.
- Based on a DSMB recommendation, this process was changed as of version 8.0 of the protocol. The basic process proceeds as described above, but once all subjects in a given cohort (n) have been enrolled, data from all prior cohorts (cohort 1, cohort 2,, cohort n-1) are used to determine the dose level of cohort n+1.
 - If enrollment is rapid such that both cohort (n-1) and cohort (n) are filled and awaiting DLT review, new subjects enrolled will be randomized to placebo until

cohort (n-1) has been reviewed. (For example, if both cohort 13 and 14 are filled and awaiting review, subjects will be randomized to placebo until cohort 13 is closed and the model is rerun to determine the dose for cohort 15.)

The MTD will be defined as the dose that would be chosen from the CRM at the final step. The study will stop once the first of the following criteria have been met:

- The maximum number of cohorts (22) has been observed.
- If at any time after half of the cohorts (11) have been observed, two consecutive iterations suggest a 15% or higher toxicity rate at the lowest dose (stop for safety).
- If the study proceeds straight to the highest dose, and then observes 9 successive cohorts at the highest dose with no observed toxicity (stop and declare highest dose the MTD).

Outcomes and Criteria for Evaluation:

- Safety monitored by physical examinations (PEs), vital signs (VS), clinical laboratory tests (i.e., chemistries, hematology, coagulation studies, and urinalysis), CT and MRI, ECGs and adverse event (AE) assessment.
 - Dose-limiting toxicities will be assessed from the first dose to 48 hours following the last dose of study treatment (unless specified below) and defined as any of the following AEs that have an attribution of "related" to study treatment (possibly, probably, and definitely):

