Matching placebo will be 0.9% sodium chloride in water, visually indistinguishable from the test product. Placebo, 100 mL, will be administered in the same manner as the active product.

Following completion of tPA infusion or initiation of mechanical thrombectomy (arterial puncture), whichever is sooner, eligible adult subjects will receive 3K3A-APC or matching placebo 30 to 120 minutes later given as a 15-minute infusion. Subjects will receive another 15-minute infusion of 3K3A-APC or placebo every 12 hours (+/- 1 hour) for up to 5 total infusions.

Study and Treatment Duration

Each subject will be followed for 90 days in this study. With an expected enrollment rate of 0.3 subjects/site/month in approximately 15 NeuroNEXT sites, it is anticipated that the study will take up to 28 months to enroll, which includes the observation window after each of the 22 cohorts to assess for DLTs. Subjects will be considered for the study after beginning tPA administration or mechanical thrombectomy or both for moderate to severe acute ischemic stroke. Eligible subjects will receive 3K3A-APC or placebo every 12 hours for up to 5 doses (approximately 3 days), or until discharge from the hospital, whichever occurs first. Subjects will be monitored for safety evaluations through Day 7 and are expected to be seen on Days 7, 14, 30 and 90 for safety and outcome evaluations.

Sample Size and Population

Sample Size:

The study will enroll approximately 115 subjects, which includes the planned 88 subjects in groups of four (each cohort will include one placebo and three treated subjects) and additional placebo subjects who will be enrolled during safety review pauses. While placebo is not needed to determine the MTD, a placebo group has been included in order to conduct secondary analyses to examine for a reduction of tPA/mechanical thrombectomy-related bleeds by central read and to obtain preliminary efficacy data that may be useful for the planning of future studies.

Randomization Scheme:

Subjects will be randomized using an interactive web response system (IWRS) to either 3K3A-APC or placebo. There are 22 groups of four subjects planned, but fewer may be enrolled should the study meet either of the early stopping criteria. During the DLT review periods, subjects may be assigned to placebo. The additional placebo subjects will be closely monitored and their enrollment may be discontinued should the number enrolled exceed what was planned for the study. Subjects

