The monitoring of subject safety and data quality will follow the NINDS Guidelines for Data and Safety Monitoring in Clinical Trials. A Data and Safety Monitoring Board (DSMB) appointed by the NIH/NINDS will meet at approximately six-month intervals (or as determined by the NINDS) to review partially unblinded study data provided by the study statistician. This committee will monitor rates of adverse events and endpoints in the trial and will monitor the performance of the trial. The frequency and format of DSMB meetings, reports, and guidelines for interim analysis will be agreed upon prior to study subject enrollment. The PPI will appoint an IMM to review all adverse events, in a blinded fashion. The IMM will perform a review of Day 1-7 data (including non-serious AEs) on Day 8 to look for missed DLTs. During that same Day 8 review the IMM will evaluate for safety and for neuroworsening all AEs that have been reported. Any non-serious AEs that occur during the DLT period but are not reported until after the Day 8 review will be evaluated in real time by the

IMM for safety, neuroworsening, and DLTs. Any non-serious AEs that occur after the DLT observation period can be reviewed on a quarterly basis or sooner at the discretion of the IMM. In addition the IMM will review all events that meet the regulatory definition of a Serious Adverse Event (SAE), upon receipt of notification via the Electronic Data Capture (EDC) system, for safety, neuroworsening and DLTs. See the Safety Management Plan for more detail.

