After each group of subjects has been treated, and their status observed as to whether or not each had a DLT, the posterior mean of *a* will be calculated. Based upon that estimate, \hat{a} , the highest dose with estimated toxicity probability, $\psi(x_i^*, a)$ less than or equal to 10% will be allocated to the next group of subjects needing treatment assignment. If this dose is more than one level higher than the previous dose allocated to a cohort, the dose will only be increased one level. After the final group of subjects is enrolled, the final MTD will be defined as the highest dose with estimated toxicity probability less than or equal to the target toxicity level of 10%.

Hence, the design will proceed as follows:

- Enroll the first 4 subjects into cohort 1.
 - Treat one of the four subjects (chosen randomly) with placebo.
 - $_{\odot}$ Treat the other three subjects with the lowest dose: 120 µg/kg.
 - Observe the number of subjects (out of the three treated subjects) that have a DLT per study definition. Any given subject who receives only one dose of study drug and does not experience a DLT will not be included in the CRM calculation (i.e. two or more doses will need to be administered to be included).
 - Based upon the observed information from the three treated subjects, refit the assumed dose-response curve.
- Initially (through version 7.1. of the protocol), the re-estimated dose-response curve using all cohorts enrolled to date was then used to determine the highest dose level of the four under consideration that has an estimated probability of toxicity less than or equal to 10%

- The next cohort of subjects is treated at the dose level specified above unless the chosen dose level is more than one level higher than the current level. If so, treat the next cohort of subjects at the next dose level above the current level.
- Based on a DSMB recommendation, this process was changed as of version 8.0 of the protocol. The basic process proceeds as described above, but once all subjects in a given cohort (n) have been enrolled, data from all prior cohorts (cohort 1, cohort 2,, cohort n-1) are used to determine the dose level of cohort n+1.

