Four dose levels will be considered for this study: 120, 240, 360, and 540 µg/kg. Following completion of tPA infusion, or initiation of mechanical thrombectomy (arterial puncture), whichever is sooner, eligible adult subjects will receive 3K3A-APC or placebo 30 to 120 minutes later given as a 15 minute infusion. Subjects will receive another 15 minute infusion of study treatment every 12 hours (+/- 1 hour) for up to 5 total doses (or until discharge, whichever occurs first). It is preferable not to skip doses of study drug, and should a dose need to occur outside of the +/- 1 hour window (which will be reported as a protocol deviation), doses should never be given within 8 hours of one another.

For the purposes of this study, we assume an established background symptomatic intracerebral hemorrhage (SICH) rate of 3-6% (Wahlgreen et al, 2007; Hacke et al, 2008; Berkhemer et al, 2015; Campbell et al, 2015; Goyal et al, 2015; Saver et al, 2015). Correspondingly, this study aims to identify the highest dose with a DLT rate of 10% or less. Subjects will be enrolled to 3K3A-APC dose cohorts in groups of four (three to specified treatment dose and one to placebo). Subjects will generally be enrolled at the dose estimated from the model at that time, based on the assumed original dose-response model and all prior observed data to date, as the highest dose with a DLT rate of 10% or less. However, the initial cohort will start at the lowest dose (120 µg/kg) and the dose level may be escalated by no more than one dose between consecutive cohorts (there are no restrictions on dose level de-escalation). Intra-subject dose modification is not permitted during the study. After the final group of subjects is enrolled, the final MTD will be defined as the highest dose with an estimated toxicity probability less than or equal to the target toxicity level of 10%.

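### Since version 8.0 the CRM runs one cohort behind, but the one-level escalation cap is still counted from the last allocated cohort, so the written rule does not tie escalation to reviewed doses

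*SAP*

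**What the plan says.** The lag came in mid-trial: "Based on a DSMB recommendation, this process was changed as of version 8.0 of the protocol" (SAP 7). Once cohort n is filled, the results of cohorts 1 to n-1 "are used to determine the dose level of cohort n+1" (Protocol 8.1.1). Through version 7.1 all cohorts to date were used. The one worked example reads "if both cohort 13 and 14 are filled and awaiting review, subjects will be randomized to placebo until cohort 13 is closed" (SAP 7), after which the dose for cohort 15 is set.

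The cap has three wordings, none of them tied to reviewed data:
- SAP 7, and Protocol 8.1.1 in nearly the same words: "If this dose is more than one level higher than the previous dose allocated, the dose will only be increased one level".
- SAP 1: "the dose level may be escalated by no more than one dose between consecutive cohorts".
- Protocol synopsis, Design, and SAP 7: the model's choice applies "unless the chosen dose level is more than one level higher than the current level".

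Three other places bear on the gap. Protocol 8.1.1 holds a dose assignment until potential DLTs have been reviewed. SAP 10.6 holds the following cohort until all four subjects of a cohort, not further identified, have passed Day 8. Protocol 3.1.2 feeds a confirmed DLT into the CRM for the next cohort that needs a dose.

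**The concern.** Before version 8.0 the last allocated cohort was also the last one in the model, so a cap counted from it kept escalation within one level of the data. The lag separates the two. Cohort n is now filled but not in the model, and the cap still counts from it. A sequence without DLTs can then climb one level per cohort while the model trails behind. The stake is exposure during early escalation, in a trial whose DLTs include symptomatic intracranial hemorrhage. A second issue is whether Table 5, which is offered in support of the lagged design, simulates the rule as worded.

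**Working it through.** **1. What the text permits.** Let cohort n-1 (120 µg/kg) be closed without a DLT and cohort n (240) be filled but not closed. The model is ψ = p^a with prior toxicities 5/7/9/11% (SAP 7). The prior on a is not given; assume exponential(1). After 0/3 DLTs at 120:

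â = ∫a·e^(-a)(1-0.05^a)³da / ∫e^(-a)(1-0.05^a)³da = 0.863/0.578 = 1.49

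The estimates p^1.49 are 1.1/1.9/2.7/3.7%. A lognormal prior (sd 1.0) gives 1.3% at 540. The model therefore points to 540 and only the cap binds. Counted from cohort n, it allows 360, two levels above the only dose in the CRM. Once 360 has been reviewed, a two-level gap is impossible.

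**2. How often, by first lagged cohort.** Simulated trials: three treated per cohort, up to 22 cohorts, SAP 7 stopping rules, cap as written. The table gives the share with at least one cohort two levels above the highest dose in the CRM, in scenarios 1 to 4. Ranges cover both priors and both allocation rules (highest dose at 10% or less; closest to 10%).

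| Lag first used for cohort | Share of trials |
|---|---|
| 3 | about 90-95% |
| 4 | about 78-90% |
| 5 | about 5-19% |
| 6 | 0 to about 15%, depending on prior and rule |
| 7 or later | 0% (all six scenarios) |

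**3. When the lag may have begun.** The synopsis gives an "expected enrollment rate of 0.3 subjects/site/month in approximately 15 NeuroNEXT sites", so 0.3 × 15 = 4.5 subjects per month. Six months yield 27 subjects, or 6.75 cohorts. From 22 cohorts in 28 months, the figure is 22/28 × 6 = 4.7. The DSMB "will meet at approximately six-month intervals (or as determined by the NINDS" (Protocol 3.1.3). If the recommendation came at a first six-month meeting (an assumption), about 5 to 7 cohorts were already filled and the share is 0 to about 15%. One or two months for amendment approval would move the start to about cohort 7 or later, where it is 0%.

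**4. Table 5.** In scenario 1 both CRM columns total 61.0 subjects. A no-DLT stop at 12 cohorts (the number in SAP 9.2) gives 66 - 30 × 0.95^36 = 61.3, so that stop is used here. With the exponential(1) prior and closest-to-10% allocation, the unlagged column is reproduced closely (largest cell difference 0.3 to 1.4 subjects across runs).

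For the lagged column, take a DLT-free run of 12 cohorts with cohort 2 held at 120:
- Unlagged: 120, 240, 360, then 540.
- Lagged, written cap: 120, 120, 240, 360, then 540.
- Lagged, reviewed-data cap: 120, 120, 240, 240, 360, 360, then 540.

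Lagged minus unlagged subjects, scenario 1:

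| | 120 | 240 | 360 | 540 |
|---|---|---|---|---|
| Table 5 | +3.4 | +3.6 | +2.6 | -9.6 |
| DLT-free, written cap | +3 | 0 | 0 | -3 |
| DLT-free, reviewed-data cap | +3 | +3 | +3 | -9 |
| Simulated, written cap | +3.1 to +4.0 | +0.3 to +0.8 | +0.2 to +0.5 | -4.1 to -4.8 |
| Simulated, both limits (see fix) | +3.3 to +3.9 | +2.9 to +3.4 | +2.3 to +2.7 | -9.2 to -9.5 |

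The simulated differences cover both priors and both allocation rules. For the absolute fit (exponential(1) prior, closest-to-10% allocation, 12-cohort stop), the summed difference over the 24 lagged cells is about 4 to 8 with a reviewed-data cap and about 41 to 48 with the written cap. A cap from the last reviewed cohort and the two-limit cap fit about equally well. Under the written 10%-or-less rule the absolute allocations match neither cap.

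**5. Effect on the result.** MTD selection differs by at most 1.5 percentage points between the caps.

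**The case against.** The strongest reply is that the condition is probably not met. The unlagged process is described in the past tense through version 7.1, the change needed a DSMB recommendation and an approved amendment (Protocol 6.4.6), and the sole example concerns cohorts 13 to 15. This stands, and it makes the high shares for cohorts 3 and 4 illustrations of the wording rather than likely events.

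Second, other safeguards run alongside. Protocol 3.1.2 can be read as carrying a confirmed DLT in cohort n into the next assignment. Arrivals average 30.4/4.5 = 6.8 days apart and the DLT window is about 4 days (48 hours of dosing plus 48), so usually only the last one or two subjects of cohort n are still under observation when it fills. This reduces the risk. It does not close the gap: reviewing the DLTs already suspected is not the same as completing a cohort. SAP 10.6 either means the immediately preceding cohort, which contradicts the 13/14/15 example, or means cohort n-1, which leaves the gap open.

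Third, the plan promises only one level between consecutive cohorts and keeps that promise. All doses also lie within the Phase 1 range: 540 µg/kg for five doses produced no serious adverse events, though in healthy volunteers (Protocol 2.5). Both points are correct.

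Fourth, the Table 5 inference rests on an assumed prior, allocation rule and stop. That also stands. It supports a question to the sponsor, not a finding of error.

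**Conclusion.** The wording has a real but minor gap. As written since version 8.0, the rule does not stop a dose two levels above the highest dose in the CRM. The gap matters only if the lag began before about cohort 7; with a later start exposure is nil, and MTD selection hardly moves in any case. Table 5's lagged column appears to describe a more cautious rule than the text. That conclusion rests on the exponential(1) prior, closest-to-10% allocation and the 12-cohort stop, and it cannot tell the two forms of reviewed-data cap apart.

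A reader might infer that subjects in this trial were dosed two levels ahead of the data, or that Table 5 is wrong. The documents support neither. They do not state the first lagged cohort, and what they do say points to a late switch. The SAS program mentioned in SAP 7 is not included; if it already limits dosing to reviewed levels, only the text needs correction.

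**What to change.** - Keep the limit of one level between consecutive cohorts and add: 'and no more than one level above the highest dose with a cohort already reviewed and entered in the CRM'. Place it in the Protocol synopsis, 3.1 and 8.1.1 and in SAP 1 and 7, and apply both limits in the dose-selection program.
- In the hold statements of Protocol 8.1.1 and SAP 10.6, name cohort n-1 as the cohort that must be reviewed before cohort n+1 is dosed.
- State which cohort was first dosed under version 8.0.
- Confirm the cap and no-toxicity stop used for Table 5's lagged column, and restate the column if they differ from the operative rule.

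Both limits are needed. A reviewed-dose limit alone allowed two-level jumps between consecutive cohorts in about 6-15% of simulated trials (lag from cohort 2, 10%-or-less rule). With both limits, two-level steps above reviewed data and two-level jumps were 0% in all six scenarios.

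The cost is one clause per section. On a DLT-free path, 540 is reached at cohort 6 instead of 4 if the lag starts at cohort 3, and at cohort 5 instead of 4 if it starts at cohort 4. There is no delay from cohort 5 on. No new simulation is needed if Table 5 is confirmed to use a reviewed-data cap.
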